8.2. Exclusion Criteria

Subjects will be excluded from study if they meet any of the following criteria:

- [8] Diagnosed with T1DM or other types of diabetes apart from T2DM (WHO Classification of Diabetes [Attachment 3](#); ADA 2014).
- [9] Have obvious clinical or radiographic signs or symptoms of liver disease (except nonalcoholic fatty liver disease), cirrhosis, acute or chronic hepatitis, or alanine aminotransferase (ALT/SGPT) and/or aspartate aminotransferase (AST/SGOT) levels $\geq 2.5X$ upper limit of normal (ULN), alkaline phosphatase $\geq 2X$ ULN or total bilirubin $\geq 2X$ ULN (with the exception of known Gilbert syndrome) as defined by central laboratory.
- [10] Have chronic kidney disease Stage 4 and higher (estimated glomerular filtration rate < 30 mL/minute/1.73m² as measured by Modification of Diet in Renal Disease [MDRD] formula) (NKF 2007) or history of renal transplantation.
- [11] Have history of more than 1 episode of severe hypoglycemia requiring assistance of another person, resulting in coma, seizures, or disorientation within the 6 months prior to Visit 1.
- [12] Have received U-500R insulin by CSII in the 3 months prior to Visit 1.
- [13] Have had a blood transfusion or severe blood loss within 3 months prior to Visit 1 or have known hemoglobinopathy, hemolytic anemia, or sickle cell anemia that is known to interfere with HbA1c measurement.
- [14] Have known allergy to human insulin preparations or excipients contained in these products or prior history of suspected antibodies to human insulin.
- [15] Are taking chronic (lasting longer than 14 consecutive days) systemic glucocorticoid therapy (excluding topical, intra-articular, intraocular, and inhaled prescriptions), or have received any systemic glucocorticoid therapy within the 4 weeks immediately prior to Visit 1.
- [16] Have an irregular sleep/wake cycle (for example, subjects who sleep during the day and work during the night), in the investigator's opinion.
- [17] Intend to participate in an extended period of fasting during the study period (for religious or other purposes).

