10.4.5. Safety Monitoring

The Lilly CRP or CRS will monitor safety data throughout the course of the study.

Lilly will review SAEs within timeframes mandated by company procedures. The Lilly CRP/CRS will, as is appropriate, consult with the functionally independent Global Patient Safety therapeutic area physician or clinical scientist, and periodically review:

- Trends in safety data
- Laboratory analytes
- AEs
- Product complaints

If a study subject experiences elevated ALT or AST $\geq 3X$ ULN, elevated total bilirubin $\geq 2X$ ULN, or alkaline phosphatase $\geq 2X$ ULN, clinical and laboratory monitoring should be initiated by the investigator. Details for hepatic monitoring depend upon the severity and persistence of observed laboratory test abnormalities. To ensure subject safety and comply with regulatory guidance, the investigator is to consult with the Lilly designated medical monitor regarding collection of specific recommended clinical information and follow-up laboratory tests.

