### 5.13.6. Laboratory Measures

As applicable per protocol, measures within the following panels will be summarized at Screening (Visit 1), Visit 4 (Week 0), Visit 13 (Week 14), and Visit 17 (Week 26) or endpoint (LOCF):

- chemistry (creatinine, uric acid)
- c-peptide
- eGFR
- lipids (total cholesterol, calculated low-density lipoprotein cholesterol [LDL-C], high-density lipoprotein cholesterol [HDL-C], triglycerides [TG], and free fatty acids [FFAs])
- liver test panel (alanine aminotransferase [ALT], aspartate aminotransferase [AST], gamma-glutamyl transferase, alkaline phosphatase)

Treatment-emergent high, low, and abnormal values will be summarized for each lab measure listed above. A treatment-emergent **high value** is defined as a value that was normal or low at baseline and subsequently found to be above the normal range at any post-baseline visit. A treatment-emergent **low value** is defined as a value that was normal or high at baseline and subsequently found to be below the normal range at any post-baseline visit. A treatment-emergent **abnormal value** is defined as a value that was normal at baseline and subsequently found to be abnormal at any post-baseline visit; however, for ALT/serum glutamic pyruvic transaminase (SGPT) or AST/serum glutamic oxaloacetic transaminase (SGOT)  $\geq 2.5X$  upper limit of normal (ULN) will be used as the abnormal threshold. The proportion comparisons between 2 treatment groups will be analyzed using Fisher's exact test.

Actual value, percentage CFBL in lipids panel (total cholesterol, calculated LDL-C, HDL-C, TG, FFAs), and CFBL in other measures will be summarized and analyzed. If only one post-baseline measurement is scheduled, then an ANCOVA model will be used; if more than one post-baseline measurement is scheduled, then an MMRM model will be used. The MMRM model will include the following fixed effects: treatment (U-500R CSII, U-500R MDI), weeks on treatment, the interaction between treatment and weeks, and the stratification factors (U-500R at entry versus other insulins, entry HbA1c  $\geq 8.5\%$  or  $< 8.5\%$ , nonusers versus users of GLP-1 receptor agonists or SGLT2 inhibitors). The model will also include the corresponding baseline measures as a covariate. The ANCOVA model will include the same fixed effects in the MMRM model but without the terms involving weeks.

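### Treatment-emergent laboratory counts in SAP 5.13.6 cannot register same-direction worsening in subjects who are already out of range at baseline, and entry admits such subjects

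*SAP*

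**What the plan says.** SAP 5.13.6 sets three categories for the listed laboratory measures and compares the arms on each by Fisher's exact test.

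- *High*: "a value that was normal or low at baseline and subsequently found to be above the normal range at any post-baseline visit".
- *Low*: "a value that was normal or high at baseline and subsequently found to be below the normal range at any post-baseline visit".
- *Abnormal*: "a value that was normal at baseline and subsequently found to be abnormal at any post-baseline visit". For ALT and AST only, 2.5 times or more the "upper limit of normal (ULN) will be used as the abnormal threshold".

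Protocol 12.2.10.6 carries the same three definitions without the ALT/AST threshold. The measures include creatinine, eGFR, ALT, AST, GGT and alkaline phosphatase. SAP 5.2 takes baseline as the last value up to randomization.

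Protocol 8.2 fixes who can enter. Criterion [9] excludes "alanine aminotransferase (ALT/SGPT) and/or aspartate aminotransferase (AST/SGOT) levels" at or above 2.5×ULN and alkaline phosphatase at or above 2×ULN. It sets no GGT limit and allows nonalcoholic fatty liver disease. Criterion [10] applies to those who "Have chronic kidney disease Stage 4 and higher", that is, eGFR below 30 mL/min/1.73 m². SAP 5.5 plans a baseline class for CKD stage 3 (eGFR 30 to below 60).

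**The concern.** Each category detects a crossing out of range. None detects further movement by a subject who has already crossed. The entry criteria admit subjects with stage 3 kidney function, moderately raised transaminases or alkaline phosphatase, and any GGT value. For these subjects a large deterioration adds nothing to the treatment-emergent counts, while a trivial crossing from the normal range does.

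The adverse event rule in SAP 5.13.3 is different: an event that worsens in severity after Visit 4 is treatment-emergent. The laboratory rule has no such limb.

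At stake is one planned between-arm safety comparison. If the arms differed in kidney or liver worsening among subjects with an abnormal baseline, the planned Fisher tests could not show it.

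**Working it through.** The plan states no figure to reproduce, so the check is of the definitions.

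**Rule.** Let *b* be the baseline and *p* a post-baseline value. For the high direction, in multiples of ULN, *high* requires b ≤ 1 and p > 1. For the low direction, in multiples of the lower limit, *low* requires b ≥ 1 and p < 1. *Abnormal* requires b within range and p outside it. If b > 1 in the high direction, both *high* and *abnormal* fail for every p. The low direction works the same way.

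**ALT/AST abnormal.** The SAP does not say whether 2.5×ULN also defines normal at baseline. Two readings are possible:

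- (a) baseline within the reference range and p ≥ 2.5×ULN;
- (b) b < 2.5×ULN and p ≥ 2.5×ULN.

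Reading (b) is the more natural one, because 2.5×ULN is also the entry limit in criterion [9].

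**Illustrative pairs** (chosen to test the rule, not trial data):

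| Measure | Baseline → worst | High or low | Abnormal |
|---|---|---|---|
| Creatinine, ×ULN | 0.9 → 1.05 | counted | counted |
| Creatinine, ×ULN | 1.3 → 3.9 | no | no |
| Alkaline phosphatase, ×ULN | 1.3 → 4 | no | no |
| GGT, ×ULN | 3 → 10 | no | no |
| eGFR | 95 → 55 | counted | counted |
| eGFR | 45 → 20 | no | no |
| ALT/AST, ×ULN | 0.9 → 3 | counted | counted on (a) and (b) |
| ALT/AST, ×ULN | 1.5 → 2.4 | no | no on (a) and (b) |
| ALT/AST, ×ULN | 1.5 → 10 | no | (a) no, (b) counted |
| ALT/AST, ×ULN | 2.6 → 10 | no | no on (a) and (b) |

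The eGFR rows assume a lower limit of 60 or 90, since the documents give none. The baseline of 45 is then 45/60 = 0.75 or 45/90 = 0.5 of the limit, below range either way. The unscored creatinine pair is a threefold rise (3.9/1.3 = 3).

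The last ALT/AST row is possible because the opening of Protocol Section 8 does not re-confirm criteria [9] and [10] at Visit 4. A Visit 4 baseline can therefore sit above the entry limit.

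**Other outputs that might fill the gap.** SAP 5.13.6 also summarizes and models change from baseline for all subjects, and SAP 5.2 includes the minimum and maximum. These show the most extreme value in an arm, not how many subjects worsened. SAP 5.13 makes listings conditional. The hepatic trigger in Protocol 10.4.5 ("If a study subject experiences elevated ALT or AST" of 3×ULN or more, or alkaline phosphatase of 2×ULN or more) has no baseline condition. It starts monitoring, however, and no table in SAP 5.13.6 uses it. Protocol 8.3.2 excepts hepatic laboratory values and does not list [10] among its discontinuation triggers, so disposition tables need not show these subjects either.

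**The case against.** The strongest reply is that worsening is not lost from the report. Change from baseline is analysed whatever the baseline, and the minimum and maximum can expose an extreme case. Clinically significant laboratory findings that lead to a diagnosis are reported (Protocol 10.4.1), and worsened events enter the TEAE tables and their Fisher tests (SAP 5.13.3). Investigators document review of each laboratory safety report (Protocol 10.5.1), the sponsor follows laboratory trends, and a DMC sees unblinded safety data. This stands, and it confines the point to the treatment-emergent counts. A reader might infer that a liver or kidney signal would be invisible; the documents do not support that. These routes still give no by-arm count of subjects whose laboratory values worsened, and the adverse event route depends on an investigator's diagnosis.

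A reader might also infer that every category needs a normal baseline, or that raised ALT/AST at entry can never be scored. Neither holds. *High* accepts a low baseline and *low* accepts a high one. On reading (b), an eligible subject who rises from between 1× and 2.5×ULN to 2.5×ULN or above is counted as abnormal. On that reading, a 3×ULN row adds little for subjects who start below 2.5×ULN.

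The affected group may also be small. Criterion [18], re-confirmed at Visit 4, excludes subjects with a label contraindication to a current antihyperglycemic agent. Its metformin example is serum creatinine of at least 1.4 mg/dL in women or 1.5 mg/dL in men. This limits raised creatinine among metformin users but leaves eGFR, alkaline phosphatase and GGT untouched.

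Finally, both arms receive the same insulin, and liver or kidney change is not a stated objective. That is a fair reason to rank the point low.

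**Conclusion.** The point holds as a minor gap in the safety analysis. Same-direction worsening from an already abnormal baseline cannot enter the treatment-emergent counts or their Fisher tests for creatinine, eGFR, alkaline phosphatase, GGT and ALT/AST *high*. For ALT/AST *abnormal* the gap depends on an unstated baseline rule. On the natural reading it closes, except for a subject whose Visit 4 value is already at or above 2.5×ULN.

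The size cannot be computed. The documents give neither baseline abnormality rates nor reference ranges, and the kidney examples assume that stage 3 eGFR lies below the laboratory's range. It is tempting to attach a percentage. With a share *b* of subjects abnormal at baseline and a relative risk *r* of marked worsening, the unscorable share is b·r/(b·r + 1 − b). That gives 0.1/(0.1 + 0.9) = 10% at b = 0.1, r = 1, and 0.9/(0.9 + 0.7) = 56% at b = 0.3, r = 3. Both inputs are assumptions, so the range says nothing about this trial. Nor do the documents show that subjects with an abnormal baseline are the likeliest to worsen. The efficacy analyses are unaffected.

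**What to change.** In SAP 5.13.6:

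1. Add a by-arm table, for all subjects regardless of baseline, of those whose worst post-baseline value reaches limits already in the protocol: ALT or AST ≥3×ULN, alkaline phosphatase ≥2×ULN, eGFR <30 mL/min/1.73 m². Compare the arms by Fisher's exact test, as for the existing categories.
2. Add baseline-to-worst shift tables for creatinine and GGT, for which the protocol has no comparable limit.
3. State that the ALT/AST threshold of 2.5×ULN defines abnormal at baseline as well as after it.

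The data are already collected and the planned analyses stay as they are. The cost is one or two more safety tables to produce and review.

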**Figure IBHD.4.1. Illustration of study design for clinical protocol B5K-MC-IBHD.**

## 5. A Priori Statistical Methods

### 5.1. Sample Size Determination

Approximately 320 subjects requiring high-dose insulin without use of GLP-1 receptor agonists or SGLT2 inhibitors (Group A) and approximately 64 to 96 additional subjects with use of GLP-1 receptor agonists or SGLT2 inhibitors (Group B) will be randomized based on a 1:1 ratio to 2 treatment arms. Approximately 240 (Group A) and 48 to 72 (Group B) subjects are expected to complete the 26-week treatment period (assuming a 25% dropout rate).

The sample size was calculated based on the first primary objective for subjects without use of GLP-1 receptor agonists or SGLT2 inhibitors (Group A). The 240 completers will provide 80% statistical power to demonstrate the noninferiority (NIM is 0.4%; SD = 1.1%) of U-500R insulin CSII versus U-500R MDI in change in HbA1c at 26 weeks at 2-sided alpha = 0.05.

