Separate efficacy analyses for primary and key secondary objectives will be conducted by either including or excluding post study treatment discontinuation data based on different purposes (see Section 5.9 and Section 5.10). In general, missing data will not be imputed, unless otherwise specified, for example, where the Last-Observation-Carried-Forward (LOCF) method or the copy reference multiple imputation method (per FDA's request) is mentioned.

Outcomes (laboratory, vital signs, weight, patient reported outcome questionnaires) measured within 5 days of last treatment dose will be considered on treatment and included in the analysis during the treatment period.

For data collected as a running record with an exact date stamp such as adverse events (AEs), SMBG, and hypoglycemia event where the dates of the measures were not tied with the date of an office visit, post-baseline data recorded at or prior to the last study drug dose date will be considered as data on treatment and included in the analysis during the treatment period.

Baseline will be the last value obtained at or prior to the randomization, unless otherwise stated.

For continuous measurements, summary statistics will include sample size, mean, median, SD, minimum, and maximum. Summary statistics for continuous measures will be provided for baseline, the actual measurements at each visit, and the change from baseline measurements to each visit. For all continuous variables, both the actual value and change from baseline (if available) will be analyzed.

An MMRM model will be used for continuous outcomes with repeated post-baseline measurements to compare treatment arms, unless otherwise noted. An ANCOVA or analysis of variance (ANOVA) model may also be used for continuous outcomes to compare treatment arms at the endpoint using the LOCF method. Treatment comparisons will be performed for the treatment difference in least squares means (LSMean). LSMean (standard error [SE]) by treatment group and visit (if applicable), the LSMean difference between treatment groups, along with 95% confidence limits of the treatment differences and the p-value for the treatment comparison will be displayed. For the change from baseline, p-value for the within-treatment difference will also be displayed.

All tests of treatment effects will be conducted at a 2-sided alpha level of 0.05, unless otherwise stated.

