### 5.13. Safety Analyses

Safety measures will include hypoglycemic events, AEs/treatment-emergent adverse events (TEAEs), body weight, vital signs (systolic and diastolic blood pressures and pulse rate), treatment exposure, and laboratory measures. In general, safety summary analyses will be done for Group A+B. However, hypoglycemic event and weight analyses assessing secondary objectives will be done for both Group A and Group A+B. All safety measures will be summarized for ARS by treatment for the 26-week treatment period. If listings are provided, they will contain data after the subjects discontinue the study treatment. For treatment comparisons of frequency and proportion of event variables (such as AEs and hypoglycemia events), Fisher's exact test will be used, unless otherwise specified.

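### Modelling arithmetic percentage change in triglycerides and free fatty acids tilts each arm's reported change toward a false rise and costs some power between arms

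*SAP*

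**What the plan says.** For the lipid panel, SAP 5.13.6 names the quantities to be summarised and analysed: "Actual value, percentage CFBL in lipids panel (total cholesterol, calculated LDL-C, HDL-C, TG, FFAs". Other laboratory measures get plain change from baseline. The model follows the number of draws: "if more than one post-baseline measurement is scheduled, then an MMRM model will be used". Protocol Attachment 1 schedules the lipid panel at Visits 4, 13 and 17, so there are two post-baseline values and the MMRM applies. On adjustment the SAP says: "The model will also include the corresponding baseline measures as a covariate". It gives no log transform, geometric mean or rank method for lipids.

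SAP 5.2 sets the general reporting rules. LSMeans and their difference are shown with 95% limits, and it adds: "For the change from baseline, p-value for the within-treatment difference will also be displayed". Testing is at the usual level: "All tests of treatment effects will be conducted at a 2-sided alpha level of 0.05, unless otherwise stated". The descriptive rule includes the median: "For continuous measurements, summary statistics will include sample size, mean, median, SD, minimum, and maximum". Under SAP 5.13, "In general, safety summary analyses will be done for Group A+B", so the lipid models use the combined population.

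**The concern.** Percentage change is not symmetric. A subject whose triglycerides double scores +100%; one whose triglycerides halve scores −50%. These two cancel on a ratio scale, yet their average is +25%. Averaged over an arm, random fluctuation alone produces a positive mean. The more a lipid fluctuates within subjects, the larger the artefact, so TG and FFA are the measures to worry about.

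Two things are at stake. First, the safety tables could show a rise in TG or FFA within an arm, apparently significant, when the distribution has not moved; that could be read as an effect of the insulin. Second, the percentage-change response is right-skewed, so a normal-theory comparison of the arms uses the data less efficiently than a log-scale one.

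**Working it through.** **The plan's own power figure.** The only one is for HbA1c. Per arm, 2 × (1.960 + 0.842)² × 1.1² / 0.4² = 118.7, so 119 per arm or 238 in total, against the stated 240; 240 / 0.75 = 320 randomised. It reproduces, but nothing comparable is given for lipids.

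**Inputs from the documents.** SAP 5.1: "Approximately 240 (Group A) and 48 to 72 (Group B) subjects are expected to complete the 26-week treatment period (assuming a 25% dropout rate"). Total completers are 240 + 48 = 288 to 240 + 72 = 312. At 1:1 that is 144 to 156 per arm.

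**Inputs assumed.** The documents give no lipid SD and no baseline-to-Week-26 correlation. I take log-normal values with log-scale SD σ from 0.4 to 0.7 for TG and FFA, 0.25 for cholesterol-like measures, and correlation ρ of 0.7 to 0.8.

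**Direction of the artefact, without a distributional assumption.** Let X be baseline and Y follow-up. If nothing has changed, in the sense that X and Y are exchangeable, then E(Y/X) = ½ E(Y/X + X/Y) ≥ 1, because a + 1/a ≥ 2 for any positive a. Baseline adjustment does not remove this: the LSMean is evaluated at the average baseline, where it estimates the mean percentage change.

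**Size under log-normality.** The within-subject log change has variance v = 2σ²(1 − ρ), and the mean percentage change is exp(v/2) − 1.

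- σ 0.4, ρ 0.8: exp(0.16 × 0.2) − 1 = 3.3%
- σ 0.4, ρ 0.7: exp(0.16 × 0.3) − 1 = 4.9%
- σ 0.6, ρ 0.7: exp(0.36 × 0.3) − 1 = 11.4%
- σ 0.7, ρ 0.7: exp(0.49 × 0.3) − 1 = 15.8%
- σ 0.25, ρ 0.7: exp(0.0625 × 0.3) − 1 = 1.9%

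**Chance of a false within-arm rise, by hand.** For σ 0.6, ρ 0.7, v = 0.216. The SD of Y/X is exp(v/2) × √(exp(v) − 1) = 1.114 × 0.491 = 0.547. With 156 subjects the standard error is 0.547/√156 = 0.0438, so z = 0.114/0.0438 = 2.60, and the chance of exceeding 1.96 is about Φ(0.64) = 0.74. The covariate removes some variance, so the adjusted figure is a little higher.

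**Simulation.** Single-visit ANCOVA with treatment and baseline, 3,000 or more runs per setting, 156 per arm, ρ 0.7. The false-rise columns assume no true change; the power columns assume a true 12% difference.

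| σ | False rise | One arm falsely significant | Power, % change | Power, actual value | Power, log |
|---|---|---|---|---|---|
| 0.25 | 1.9% | 0.26 | – | – | – |
| 0.4 | 4.9% | 0.49 | 0.97 | 0.96 | 0.98 |
| 0.5 | 7.8% | 0.66 | 0.85 | 0.81 | 0.89 |
| 0.6 | 11.4% | 0.78 | 0.68 | 0.63 | 0.74 |
| 0.7 | 15.8% | 0.86 | 0.51 | 0.46 | 0.60 |

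Repeat runs agree within about 2 points (0.87 at σ 0.7). The log analysis gives a false within-arm rise in about 0.03 of trials. At the mild end (σ 0.4, ρ 0.8) the per-arm rate is about 0.31. Both arms are falsely significant together in about 0.43 to 0.74 of trials for σ 0.5 to 0.7 at ρ 0.7, and in about 0.2 at σ 0.4.

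**Between arms.** With no true difference, the percentage-change test rejects in about 5% of trials, the same as the log test. The power loss in the table is 4, 6 and 9 points at σ 0.5, 0.6 and 0.7, and up to about 10 in repeat runs. At σ 0.4 it is about 1 point, because both analyses are near certain to detect 12%. If the effect is instead set so that the log analysis has about 80% power, the loss at σ 0.4 is about 3 points (0.761 against 0.791 with 312 completers).

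**The case against.** The strongest reply is that the percentage-change mean does not stand alone. The same SAP sentence also models the actual value, SAP 5.2 requires medians, and SAP 5.13.6 counts new out-of-range values. None of these has the ratio bias; the median percentage change is about zero when nothing has moved. This stands, and an attentive reader would have the means to spot the discrepancy. It does not remove the misleading LSMean from the table, and the actual-value model has even less power than percentage change in every TG-like or FFA-like setting above.

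The within-arm p-value is also an inference. SAP 5.2 attaches it to change from baseline, and SAP 5.13.6 separates percentage change (lipids) from plain change (other measures). Applying the rule to percentage change is the natural reading but is not stated. If no p-value is shown, the false rise in the LSMean remains and the false-significance rates do not apply.

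The size rests on assumed variability, and the simulation used one visit without stratification factors rather than the planned two-visit MMRM. Both limits stand. The direction of the artefact depends on neither.

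A reader might infer three stronger things that the documents do not support. One is that the CSII-versus-MDI comparison is biased: its type I error is about 5%. Another is that both arms will usually show a significant rise: that depends on the assumed SD and fails in the milder settings. The third is that the whole lipid panel is affected alike: at an assumed log-SD of 0.25 the false rise is only about 2%.

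**Conclusion.** The point holds for TG and FFA. Under SAP 5.13.6 the within-arm mean percentage change leans upward when nothing has changed, by about 3% to 16% for log-SD 0.4 to 0.7, correlation 0.7 to 0.8 and 144 to 156 completers per arm. If the SAP 5.2 within-treatment p-value is attached, a given arm is falsely significant in about 0.3 to 0.87 of trials instead of 0.025. The randomised comparison remains valid but can lose up to about 10 power points against a log-scale analysis; the loss is negligible to small at log-SD 0.4 or less with correlation 0.7.

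The consequence is limited. Lipids are laboratory safety measures outside H1 to H10, so neither the primary conclusion nor the sample size is touched. The change is still worth making, because the flaw is in a stated analysis and the remedy is simple.

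**What to change.** In SAP 5.13.6, for TG and FFA, model log(value) with log(baseline) as covariate in the same MMRM or ANCOVA. Report the back-transformed geometric percentage change per arm and the CSII/MDI ratio with 95% CI, in place of the arithmetic percentage-change LSMeans and any within-arm p-values on them. Extending this to total cholesterol, LDL-C and HDL-C is optional.

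The cost is a few lines of SAP text and a log transform in existing programs, with no new data. Protocol 12.2.10.6 does not specify percentage change, and Protocol 12.2.1 calls for an amendment only when a principal feature changes, so a SAP edit should be enough. The small downside is that TG and FFA results become geometric rather than arithmetic percentage changes, which a table footnote should say.
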